1.2.2 Blinded Independent Central Imaging Review

A blinded independent central review (BICR) of tumor assessment data will be performed to support the primary endpoint of investigator-assessed PFS. To facilitate BICR for PFS, all radiological data (e.g., computed tomography [CT] scan, magnetic resonance imaging [MRI], bone scan) and photographs for skin lesions obtained at baseline, during the treatment period, at the time of disease progression, and at the time of study treatment discontinuation (if not the same as disease progression) should be sent to a central imaging vendor (contracted by the Sponsor) within 2 weeks of imaging to enable retrospective BICR. Additional details about tumor assessment collections and readings will be outlined in a separate charter with the imaging vendor.

1.2.3 Data Monitoring

An external independent Data Monitoring Committee (iDMC) will be formed to evaluate safety and efficacy data from the first patient randomized until the time of the primary analysis of PFS and to conduct the interim analysis (see Protocol Section 6.9). The iDMC will monitor accumulating patient safety data approximately every 4 months during

the course of the study. The iDMC will include qualified personnel, all independent of the Sponsor, who are committed to preservation of the trial integrity and reaching valid conclusions as described in the iDMC guidance. The primary responsibilities of the iDMC will be to thoroughly review the available cumulative safety data and to make recommendations regarding modification of the conduct of study, enrollment hold, performance of additional interim safety analyses, changes to the inclusion/exclusion criteria or safety evaluation, or termination of the study if there is evidence of undue risk to the study participants.

The analyses will be conducted by an independent Data Coordinating Center and reviewed by the iDMC. Interactions between the iDMC and Sponsor will be carried out as specified in the iDMC Charter.

2. STATISTICAL HYPOTHESES AND SAMPLE SIZE DETERMINATION

2.1 STATISTICAL HYPOTHESES

The primary analysis will be a comparison of the Investigator-assessed PFS between the two treatment arms using a stratified log-rank test at an overall 0.05 significance level (two-sided).

The statistical hypothesis of this study is as follows:

- H0: PFS inavolisib plus palbociclib and fulvestrant = PFS placebo plus palbociclib and fulvestrant
- H1: PFS inavolisib plus palbociclib and fulvestrant \neq PFS placebo plus palbociclib and fulvestrant

The null and alternative hypotheses will be tested at a two-sided 0.05 significance level. The primary trial objective is to demonstrate superiority of the experimental over the control treatment.

2.2 SAMPLE SIZE DETERMINATION

Estimates of the number of events required to demonstrate efficacy with regard to PFS are based on the following assumptions:

- Two-sided log-rank test at the 0.05 level of significance
- Eighty-five percent power to detect a hazard ratio for inavolisib plus palbociclib and fulvestrant versus placebo plus palbociclib and fulvestrant of 0.65, corresponding to an improvement of 5.9 months (from 11 to 16.9 months) in median PFS for the treatment arm over the control arm
- Exponential distribution of PFS
- An annual dropout rate of 15%

With these assumptions, 194 PFS events are required to achieve 85% power for the primary analysis. The 320 patients will be enrolled over approximately 43 months and the primary analysis is expected to occur approximately 50 months after the first patient randomized.

The minimal detectable difference for the PFS hazard ratio is 0.754 (i.e., an improvement of 3.6 months (from 11 to 14.6 months) in median PFS for the treatment arm over the control arm).

3. **ANALYSIS SETS**

The participant analysis sets for the purposes of analyses are defined in [Table 3](#).

Table 3 Participant Analysis Sets

Participant Analysis Set	Description
FAS	All randomized participants; participants will be included in the analyses according to the treatment they were assigned.
SAS	All participants exposed to study treatment; participants will be analyzed according to the treatment that they actually received.
PK-evaluable	All randomized participants in the inavolisib arm who have at least one evaluable inavolisib plasma concentration.

FAS = full analysis set; SAS = safety analysis set; PK = pharmacokinetic

4. **STATISTICAL ANALYSES**

This section is a summary of the planned statistical analyses of the most important endpoints, including primary and key secondary endpoints. It also describes the sensitivity analysis related to the primary study estimand and any pre-specified subgroup analyses.

The analyses described in this SAP will supersede those specified in the protocol.

4.1 **GENERAL CONSIDERATIONS**

All efficacy analyses will be performed on the full analysis set population, unless otherwise specified. All safety analyses will be performed in the safety analysis set, unless otherwise specified.

Analyses of demographics and other baseline information will be based on full analysis set population. The baseline value of any variable will be defined as the last available data point prior to the first administration of study drug.

4.2 **PRIMARY ENDPOINT ANALYSIS**

The primary efficacy objective for this study is to evaluate the efficacy of inavolisib plus palbociclib and fulvestrant compared with placebo plus palbociclib and fulvestrant on the

basis of the Investigator-assessed PFS endpoint as defined in Section 1.1 of SAP (see Table 1).

4.2.1 Definition of Primary Estimand

Following the estimand framework introduced in the ICH-E9 addendum (ICH 2020), the attributes of the estimand built around the primary endpoint are defined as follows:

- **Population:** patients with *PIK3CA*-mutant, hormone receptor (HR)-positive, HER2-negative locally advanced or metastatic breast cancer whose disease progressed during treatment or within 12 months of completing adjuvant endocrine therapy and who have not received prior systemic therapy for locally advanced or metastatic disease, as defined in study protocol (refer to Protocol Section 4.1)
- **Variable:** PFS, defined as the time from randomization to the first occurrence of disease progression as determined by the investigator and according to response evaluation criteria in solid tumors (RECIST) v1.1, or death from any cause (whichever occurs first)
- **Treatment:**
 - Experimental: inavolisib 9-mg tablet taken PO QD on Days 1–28 of each 28-day cycle, palbociclib 125-mg capsule or tablet taken PO QD on Days 1–21 of each 28-day cycle, and fulvestrant 500 mg administered by IM injection on Days 1 and 15 of Cycle 1 and then on Day 1 of each subsequent 28-day cycle
 - Control: placebo tablet taken PO QD on Days 1–28 of each 28-day cycle, palbociclib 125-mg capsule or tablet taken PO QD on Days 1–21 of each 28-day cycle, and fulvestrant 500 mg administered by IM injection on Days 1 and 15 of Cycle 1 and then on Day 1 of each subsequent 28day cycle
- **Intercurrent events and handling strategies:**
 - Start of non-protocol anticancer therapy prior to disease progression
 - Early discontinuation from study treatment for any reason prior to a PFS event
 - Handling ICE: Following treatment policy, the above ICE will be ignored and tumor assessment data collected after the ICE will be included in the primary PFS analysis
- **Population-level summary:** Hazard ratio for PFS

4.2.2 Main Analytical Approach for Primary Endpoint

If participants have any intercurrent event(s), then the strategies defined as defined in Section 4.2.1 to handle the intercurrent events will be implemented. Data for participants without the occurrence of disease progression or death as of the clinical cutoff date (CCOD) will be censored at the time of the last tumor assessment prior to the CCOD (or at the time of randomization if no tumor assessment was performed after the baseline visit).

PFS will be compared between treatment arms using the two-sided stratified logrank test at the 0.05 level of significance.

The hazard ratio will be estimated using a stratified Cox proportional hazards model. The 95% CI for the hazard ratio will be provided. The stratification factors used will be the same as the randomization stratification factors (as entered in IxRS, Section 1.2.1). Results from an unstratified analysis (see Section 4.2.3) will also be provided as sensitivity analysis. For each treatment arm, Kaplan-Meier methodology will be used to estimate the median PFS, and the Brookmeyer-Crowley method will be used to construct the 95% CI for the median PFS. Kaplan-Meier curves will also be produced.

4.2.3 Sensitivity Analyses

The following sensitivity analysis to the primary estimand of the primary PFS after randomization will be performed:

- PFS assessed by Blinded Independent Central Review (BICR): To assess the concordance of PFS assessment by investigators' PFS analysis, as mentioned in Section 4.2.2, will be repeated based on BICR assessment. The BICR cannot evaluate patients if the baseline scans were missing hence, in such cases, data will be censored at randomization.
- PFS assessed by investigator based on unstratified analysis: To assess the impact of stratification (as entered in IxRS, see Protocol Section 6.4.1) the main analysis described in Section 4.2.2 will be repeated without stratification factors.
- PFS assessed by investigator in patients with *PIK3CA* mutation-positive status by the central test.
- Handling of missing scheduled tumor assessments: Patients who missed two or more scheduled assessments immediately prior to the date of disease progression as determined by investigator per RECIST v1.1 will be censored at the last tumor assessment prior to the missed visits.

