Patients may enroll based on eligible *PIK3CA* mutation results from testing performed by a central investigational testing site or a site local test. Local testing of blood or tumor tissue must be performed using a Sponsor-approved polymerase chain reaction (PCR)-based or next-generation sequencing (NGS) assay at a Clinical Laboratory Improvement Amendments (CLIA)- or equivalently-certified laboratory. Patients without available local test results for *PIK3CA* mutation status must submit a blood sample to determine whether an eligible *PIK3CA* mutation is present. Samples will be evaluated by the NGS-based FoundationOne[®] Liquid CDx (F1LCDx) assay, unless not implemented in specific localities. In this case, samples will be submitted to an alternative, Sponsor-designated central testing laboratory. Regardless of the testing strategy to determine a patient's tumor *PIK3CA* mutation status, all patients must provide both blood and tumor tissue for evaluation by a central investigational testing site. Demographic data will be collected on all patients who undergo screening, including those who screen fail.

Patients will be closely monitored for adverse events throughout the study treatment, and for 30 days after the final dose of study treatment or until initiation of another anti-cancer therapy, whichever occurs first. Adverse events will be graded according to NCI CTCAE v5.0. Patients who, at the 30-day safety follow-up visit, are still on anti-hyperglycemic agents for the treatment of hyperglycemia during the study treatment, and those patients with events of hyperglycemia ongoing at the 30-day safety follow-up visit, will go on to the post-treatment hyperglycemia follow-up (as defined above).

Tumor assessments will be performed to assess for response every 8 weeks (± 7 days) during the first 2 years of study treatment and every 12 weeks (± 7 days) thereafter. Patients who discontinue active study treatment for any reason other than unequivocal disease progression or death will follow the same tumor assessment schedule during the "post-treatment tumor assessment follow-up with PRO collection" period.

After study treatment discontinuation, all patients will be followed for survival and all subsequent anti-cancer therapies. These data will be collected via telephone calls and/or clinic visits approximately every 3 months until death, loss to follow-up, withdrawal of consent, or study termination by the Sponsor, whichever occurs first.

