At screening, a CT or MRI scan of the brain is required to confirm no progression in patients with previously treated brain lesions; the scan must be within the screening window and ≥ 4 weeks after the completion of radiotherapy. For all other patients, brain scans should be acquired if clinically indicated. At subsequent tumor assessment timepoints, brain scans should be acquired if disease was present at baseline or if clinically indicated.

A documented standard-of-care tumor assessment performed within 28 days prior to Cycle 1, Day 1 may be used for the screening assessment provided it meets the above requirements. Tumor assessments should be performed on schedule (approximately every 8 weeks [± 7 days] for the first 2 years after randomization, and every 12 weeks [± 7 days] thereafter) as described in [Appendix 1](#), regardless of dose delay or early discontinuation, until disease progression. Patients who discontinue study treatment for any reason other than disease progression or death will continue to undergo tumor-response evaluations until progressive disease or the initiation of another anti-cancer therapy, whichever occurs first. At the investigator's discretion, scans may be repeated at any time if progressive disease is suspected.

Patients who have demonstrated control of their systemic disease (defined as having received clinical benefit [i.e., a PR, CR, or SD for ≥ 3 months]), but who have developed brain metastases that are treatable with radiation, will be allowed to continue to receive study treatment until they either experience systemic progression of their disease and/or further progression in the brain (based on investigator assessments).

To ensure a valid comparison of tumor data and uniformity in the assessment of tumor response during the study, the following procedures must be implemented at the study site:

- All lesions identified at baseline (target and non-target) are to be reassessed using the same method throughout the course of the study.

- All radiologic data (CT scans, MRI scans, bone scans, etc.) obtained for all patients enrolled at the center should be reviewed by the local radiologist who, together with the investigator, will determine the local assessment of response and progression.

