1.1 OBJECTIVES AND ENDPOINTS

This study will evaluate the efficacy, safety, and pharmacokinetics of inavolisib in combination with palbociclib and fulvestrant compared with placebo plus palbociclib and fulvestrant in patients with *PIK3CA*-mutant, HR-positive, HER2-negative locally advanced or metastatic breast cancer whose disease progressed during treatment or within 12 months of completing adjuvant endocrine therapy and who have not received prior systemic therapy for locally advanced or metastatic disease. Specific primary and secondary objectives and corresponding endpoints for the study are outlined in [Table 1](#) and [Table 2](#). For details on exploratory objectives and endpoints, refer to Section 4.4

Table 1 Primary and Secondary Objectives and Corresponding Estimands

Primary Objective(s)	Estimand Definition

Evaluate the efficacy of inavolisib plus palbociclib and fulvestrant compared with placebo plus palbociclib and fulvestrant on the basis of progression free survival (PFS)	
Population: patients with PIK3CA-mutant, hormone receptor (HR)-positive, HER2-negative locally advanced or metastatic breast cancer whose disease progressed during treatment or within 12 months of completing adjuvant endocrine therapy and who have not received prior systemic therapy for locally advanced or metastatic disease, as defined in study protocol (refer to Protocol Section 4.1)Endpoint: PFS, defined as the time from randomization to the first occurrence of disease progression as determined by the investigator according to RECIST v1.1 or death from any cause (whichever occurs first)Treatment:
Experimental: inavolisib 9-mg tablet taken PO QD on Days 1–28 of each 28-day cycle, palbociclib 125-mg capsule or tablet taken PO QD on Days 1–21 of each 28-day cycle, and fulvestrant 500 mg administered by IM injection on Days 1 and 15 of Cycle 1 and then on Day 1 of each subsequent 28-day cycle

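### The missed-assessment sensitivity analysis for PFS censors late-detected progressions but not deaths after the same gap in scans, so it is incomplete

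*SAP*

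**What the plan says.** SAP 4.2.3 lists four sensitivity analyses for the primary endpoint. The one on missing scheduled tumor assessments applies to "Patients who missed two or more scheduled assessments immediately prior to the date of disease progression as determined by investigator per RECIST v1.1"; these patients "will be censored at the last tumor assessment prior to the missed visits". Its trigger names investigator-assessed progression and nothing else.

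The endpoint is broader. SAP 1.1 (Table 1) and SAP 4.2.1 define PFS as time to investigator-assessed progression or death from any cause, whichever comes first. Under SAP 4.2.2, the main analysis censors only patients who have had neither event by the cutoff, at their final scan before it. A death is therefore an event however long the preceding gap in scans.

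Scans are planned "approximately every 8 weeks [± 7 days] for the first 2 years after randomization, and every 12 weeks [± 7 days] thereafter" (Protocol 4.5.5). Patients who stop study treatment without progression "will continue to undergo tumor-response evaluations until progressive disease or the initiation of another anti-cancer therapy, whichever occurs first". Survival is still tracked when scans end: "After study treatment discontinuation, all patients will be followed for survival and all subsequent anti-cancer therapies" (Protocol 3.1.1), about every 3 months.

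NPT before progression and early treatment discontinuation are handled by treatment policy in the primary estimand: "the above ICE will be ignored and tumor assessment data collected after the ICE will be included in the primary PFS analysis". SAP 4.2.4 adds two supplementary analyses for NPT. One censors at the last disease assessment before NPT; the other counts the start of NPT as the PFS event.

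**The concern.** When progression is first seen after a long gap, its true date lies somewhere inside the gap, and the recorded date may be too late. That is the usual reason for censoring at the last scan before the gap. A death after the same gap raises a closely related problem. The date of death is exact, but an earlier progression may have gone unseen, in which case the PFS time is again too long. The rule treats these two events differently, and the SAP gives no reason.

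At stake is how a reassuring result from this analysis can be read. It would show that late-detected progressions do not drive the hazard ratio. It would say nothing about deaths after missed scans, and for those without recorded NPT no other planned analysis does so.

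**Working it through.** **1. Does any other text extend the rule to deaths?** No.
- SAP 4.2.3, BICR analysis: repeats the main analysis on central reads and adds no gap rule for deaths.
- SAP 4.2.3, unstratified and central-*PIK3CA* analyses: change the stratification or the population, not the censoring.
- SAP 4.2.4, hypothetical and composite analyses: act only on NPT.
- Protocol 6.4.1: refers further sensitivity analyses to the SAP.

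**2. Which deaths after a gap remain uncovered?**
- *After recorded NPT:* covered by SAP 4.2.4. Under Protocol 4.5.5, scans after treatment discontinuation end when new therapy starts, so later visits may not be scheduled and may not count as missed.
- *After symptomatic deterioration:* this is a reason to stop treatment (Protocol 4.6.1) but is not RECIST progression (Protocol 5.3.5.9, Appendix 11). Scans remain due, and a very ill patient may miss them and die. Uncovered.
- *After refused or missed scans for other reasons:* uncovered.
- *After withdrawal:* scans stop, but survival status may be obtained from public records (Protocol 4.6.2). Uncovered, provided those visits count as missed.

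**3. How long is the gap?** With two consecutive scans missed, the nominal time since the last scan is at least 2 × 8 = 16 weeks in the first 2 years, and 3 × 8 = 24 weeks by the time the next scan is due. Afterwards the figures are 2 × 12 = 24 and 3 × 12 = 36 weeks.

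**4. The plan's own figure.** SAP 2.2 gives 194 events for HR 0.65, two-sided α 0.05, power 85% and 1:1 allocation. Schoenfeld: d = 4(z₀.₉₇₅ + z₀.₈₅)² / (ln HR)² = 4(1.960 + 1.036)² / (−0.4308)² = 193.5, rounded up to 194. This reproduces. Power at 194 events is Φ(½√194 × 0.4308 − 1.960) = 85.1%.

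**5. What would censoring these deaths cost in this analysis?** The documents give no count, so the share is an assumption. The same power formula is used with the remaining events.

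| Assumed share of 194 | Deaths censored | Events left | Power at HR 0.65 |
|---|---|---|---|
| 1% | 2 | 192 | 84.7% |
| 3% | 6 | 188 | 84.0% |
| 5% | 10 | 184 | 83.2% |
| 10% | 19 | 175 | 81.3% |

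**6. How far could the hazard ratio move?** This is a crude exponential illustration. It uses medians of 11 and 16.9 months, uniform accrual over 43 months, cutoff at month 50 and 15% annual dropout, scaled to 194 events. That gives 107.1 events over 1,699.6 patient-months (control) and 86.9 over 2,121.7 (inavolisib), so HR = (86.9/2,121.7)/(107.1/1,699.6) = 0.65. Each censored death removes one event and at least 16 weeks (16/52 × 12 = 3.69 months) of exposure. Six deaths, all in control, give (86.9/2,121.7)/(101.1/1,677.5) = 0.680.

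| Deaths censored | All in control | All in inavolisib | Split evenly |
|---|---|---|---|
| 6 | 0.680 | 0.612 | 0.645 |
| 10 | 0.701 | 0.585 | 0.641 |

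**The case against.** The strongest defense is that keeping deaths as events is deliberate and sound. A death date is known, death is part of the endpoint, and the estimand follows treatment policy. Censoring a patient who stopped attending scans and then died is likely to be informative. The SAP labels the analysis only as handling missing assessments and does not promise to test every event after a gap. All of this stands as a reason why either convention can be defended. It does not explain why possible unseen progression is tested for one kind of event and not the other, and the SAP does not say that the choice was intended.

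A reader might infer more than the documents support, in three ways.

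- *That the main problem is death long after scans stop at new anti-cancer therapy.* SAP 4.2.4 gives that situation two dedicated analyses. Because those visits may not be scheduled, adding death to the trigger might not reach them anyway.
- *That the number affected can be simulated.* Suppose scans stop before progression in 5–15% of patients per year and median survival afterwards is 18–30 months; neither figure is in the documents. With the planned 15% dropout, about 4 to 15 of some 189–197 PFS events are then deaths more than 16 weeks after the last scan. Leaving dropout out inflates this to about 5 to 19 of 217–227. Both ranges pool deaths after NPT with the rest, so neither sizes the uncovered group.
- *That the analysis is uninformative.* It still tests late-detected progressions. Nor do the documents show that deaths after a gap would differ by arm; the trial is double-blind.

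**Conclusion.** The point holds in a limited form. On its wording, the missed-assessment analysis leaves deaths after two or more missed scheduled scans as events, although the endpoint includes death and unseen progression is possible in the same gap. For deaths without recorded NPT, no other planned analysis fills this hole.

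The number of such deaths cannot be derived from the documents and is probably small. If they are balanced between arms, the illustration moves the hazard ratio by about 0.01 or less. If 6 to 10 fell in a single arm, it would move by about 0.03 to 0.065. These figures rest on exponential PFS, the planned accrual and dropout, and assumed counts. This is a cheap improvement to one sensitivity analysis. The primary analysis, the 194-event target, the stated power and the type I error are not affected.

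**What to change.** In the missed-assessment item of SAP 4.2.3, add *or death* after disease progression in the trigger, and censor both kinds of event at the last tumor assessment before the missed visits. State whether visits after NPT start, or after withdrawal, count as missed. Define how missed visits are counted across the change from 8-week to 12-week scans and the ±7-day window. If the sponsor prefers to keep deaths as events, the SAP should say so and give the reason.

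The cost is a few words, a few events fewer, and some potentially informative censoring, all confined to this one analysis. It adds no data collection and has no consequence for alpha.
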